5.2 Safety Assessment Criteria

- All AEs which is occurred at least once after administration of Trajenta.

6. Statistical Analyses

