3.2 DISCUSSION OF STUDY DESIGN

This is a single arm study with linagliptin.

Loss to follow up

All efforts will be made to minimize loss to follow up, particularly in the tracking of lost patients. To the extent possible, occurrence of adverse event, at minimum, for patients lost to follow up will be obtained. This allows assessing the impact of informative censoring due to treatment discontinuation. Also, patients lost to follow up will be characterized compared to the remaining patients and reason and time point of loss to follow up will be evaluated.

Channeling bias

Channeling bias can occur due to preferential prescribing in relation to different risks for the events of interest: e.g., if linagliptin would be more often prescribed to higher risk patients compared to other treatments, higher incidences of outcome events were then expected in the linagliptin group.

Confounding

As in any observational study, confounding may affect the estimation of associated between drug exposure and outcome of interest and statistical techniques. However, as only major confounders for selected research questions can be captured, residual (unmeasured) confounding may remain.

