5.1.2.2 Adverse event and serious adverse event reporting

All adverse events occurring from the start of Trajenta treatment up to 7 days after last follow-up visit need to be collected, documented and reported to the sponsor using the AE reporting form of eCRF (Attachment 1). All SAEs must be reported with details of non-serious AEs occurring at the same time, within 24 hours of occurrence via telephone/fax to the Clinical Safety Officer (CSO) of BI Korea using the SAE report form (Attachment2). If any new or further information to these events is available, a follow-up SAE report has to be sent to BI. All SAEs and non-serious AEs must include a causal relationship assessment from the physician.

All other Adverse Events must be reported using eCRFs within 2 weeks to the Sponsor.

Contact details:

Clinical Safety Officer

Tel: [REDACTED]

Fax: [REDACTED]

Address: [REDACTED]

Pregnancy

Rarely, patients taking part in regulatory non interventional studies can get pregnant. Once a patient enrolled into the study and exposed to Trajenta becomes pregnant, the NIS physician will stop the drug and report immediately to the sponsor. Drug exposure during pregnancy has to be reported immediately (within 24 hours or next business day, whichever is shorter) to CSO. Furthermore, the details of all the drugs to which the patient exposed at the time of pregnancy will be recorded. The outcome of the pregnancy associated with the drug exposure will be assessed. In the absence of an (S)AE, only the Pregnancy Monitoring Form (Attachment 3) for NIS, not the SAE form is to be completed.

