5.2 EFFECTIVENESS

5.2.1 Endpoint(s) of effectiveness

The main effectiveness endpoint in this study is the change from baseline in HbA_{1c} after 24 weeks of treatment.

The other effectiveness endpoints are the following:

- Occurrence of treat to target effectiveness response, that is an HbA_{1c} under treatment of < 6.5% after 24 weeks of treatment.
- Occurrence of relative effectiveness response (HbA_{1c} lowering by at least 0.5% after 24 weeks)
- Change from baseline in fasting plasma glucose (FPG) after 24 weeks of treatment

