5.1 Effectiveness Assessment Criteria

- The change from baseline to last visit[†] of HbA1c
- Achievement rate of target effectiveness (HbA1c of < 6.5% at last visit)
- Achievement rate for target of reduction (At least 0.5% HbA1c lowering at last visit)
- The change from baseline to last visit of FPG
- Final effectiveness assessment

Defines the final effectiveness assessment (Improved, No changed, Worsened, Uevaluable) based on both HbA1c and FPG that measured at baseline and last visit. The final effectiveness assessment is as the following criteria:

- Improved: In case the symptoms, such as symptoms of improvement or maintenance[†], are judged
 - I. In the last visit compared to the baseline, in case the both HbA1c and FPG are maintained or decreased
 - II. In the last visit compared to the baseline, in case the HbA1c is maintained or decreased and the FPG is increased
 - III. In the last visit compared to the baseline, in case the HbA1c is increased and the FPG is maintained or decreased
- No changed: In case there is no significant change between baseline and last visit, that is, in case it is not judged to be maintenance effect
 - I. In the last visit compared to the baseline, in case the HbA1c is increased, but the FPG is unknown
- Worsened: In case the symptoms are worse in the last visit compared to the baseline
 - I. In the last visit compared to the baseline, in case the both HbA1c and FPG are increased
- Not evaluable: In case the collected information is insufficient and the final effectiveness

	CONFIDENTIAL :	Last Update Date
	THIS DOCUMENT AND INFORMATION CONTAINED HEREIN IS PROPRIETARY TO COMPANY AND IS NOT TO BE DISCLOSED WITHOUT THE WRITTEN PERMISSION OF COMPANY.	21-AUG-2017
STATISTICAL ANALYSIS PLAN(V3.0)		

assessment can not be classified as 'Improved', 'No changed' or 'Worsened'

† Maintenance: In case the symptoms are likely to worsen when the administration of Trajenta is interrupt, or, in case the same effect is continue when replacing to existing drugs, etc.

‡ Last visit: The last visit point that measured HbA1c after administration of Trajenta

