6.5% at last visit and whose HbA1c lowering is at least 0.5% at last visit will be calculated. Additionally, the difference of FPG between baseline and last visit shall be analyzed with paired t-test.

- ① All of effectiveness analysis set
- ② Short-term effectiveness analysis set (Administration of Tragenta less than 24 weeks)
- ③ Long-term effectiveness analysis set (Administration of Tragenta for 24 weeks or more)
- ④ Subjects in effectiveness analysis set who administered DPP-4 inhibitor before administration of Tragenta
- ⑤ Subjects in effectiveness analysis set who did not administer DPP-4 inhibitor before administration of Tragenta

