6.3.2 Adverse Events by Preferred Terms

All AEs recorded in the CRF will be classified by body organs and terms under the classification standard of MedDRA terms, and all AEs excluding the AEs where causal relationship with Trajenta is “Unlikely” will be treated as AEs which causality cannot be excluded (hereafter “Adverse Drug Reaction(ADR)”).

For subjects to whom AE occurred, the incidence proportion of AEs and the number of AEs will be summarized.

Details are as follows.

- ① The frequency and percentage of the number of AEs according to serious adverse event, intensity, outcome of the event, action taken, causality, therapy of the event will be calculated.
- ② All AEs will be classified into the preferred terms according to serious adverse event, intensity, outcome of the event, action taken, causality, therapy of the event. The frequency and percentage of the number of each AE will also be calculated.
- ③ The number of subjects and the number of AE/ADR, Serious AE/Serious ADR, unexpected AE/ADR, unexpected Serious AE/unexpected Serious ADR will be calculated according to the preferred terms. In this case, the following subgroups are presented separately. Also, the incidence proportion and its 95% confidence interval will be estimated.
 - All of safety analysis set
 - Short-term effectiveness analysis set (Administration of Trajenta less than 24 weeks)
 - Long-term effectiveness analysis set (Administration of Trajenta for 24 weeks or more)
 - Subjects in effectiveness analysis set who administered DPP-4 inhibitor before administration of Trajenta
 - Subjects in effectiveness analysis set who did not administer DPP-4 inhibitor before administration of Trajenta
- ④ Preferred terms of Serious AE/Serious ADR, unexpected AE/ADR will be presented respectively according to the proportion of AE in the local product document.
- ⑤ For subjects excluded from the safety analysis set[†], the number of subjects and the number of AE/ADR, Serious AE/Serious ADR, unexpected AE/ADR, unexpected Serious AE/unexpected Serious ADR will be calculated according to the preferred terms. Also, the incidence proportion and its 95% confidence interval will be estimated.

[†]Subject excluded from safety analysis set: ‘Subjects who have not taken Trajenta’ and ‘Follow-up failure’ of patients excluded from safety analysis sets will be excluded (Reflecting the Ministry of Food and Drug Safety (MFDS) guideline).

	CONFIDENTIAL :	Last Update Date

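### AEs and HbA1c values are counted without regard to whether the patient is still on Trajenta, and the SAP drops the protocol's on-treatment condition from the <6.5% response

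*SAP*

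**What the plan says.** **Adverse events.** The safety criterion in SAP 5.2 is "All AEs which is occurred at least once after administration of Trajenta". Nothing closes that period at or near the last dose. Collection under Protocol 5.1.2.2 is tied to visits: "All adverse events occurring from the start of Trajenta treatment up to 7 days after last follow-up visit need to be collected".

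**HbA1c.** SAP 5.1 defines the value to be analysed as "Last visit: The last visit point that measured HbA1c after administration of Trajenta". Being on drug at that visit is not required.

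**Target response.** Protocol 5.2.1 defines the response as an HbA1c "under treatment of < 6.5% after 24 weeks of treatment", and Protocol 7.3.3 repeats the on-treatment condition. The SAP 5.1 counterpart, "Achievement rate of target effectiveness (HbA1c of < 6.5% at last visit", has no such condition.

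**Subgroups.** SAP 6.2 reports responder rates and FPG change in a "Short-term effectiveness analysis set (Administration of Tragenta less than 24 weeks". SAP 6.3.2 uses the same cut for AEs by preferred term: "Short-term effectiveness analysis set (Administration of Trajenta less than 24 weeks". SAP 6.1 also lists long-term administration (24 weeks or more) among the baseline characteristics. It is therefore a factor in the HbA1c tests of 6.2 and the AE comparisons of 6.3.1.

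**What is not there.** None of the tables listed in SAP 7.3 and 7.4 separates events or values on drug from those after the last dose.

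**The concern.** The primary objective is the safety profile of Trajenta. Suppose a patient stops at week 4, changes to another agent and has an event at week 20. If that patient is still under observation, the event enters the AE incidence exactly as an on-drug event does. The same patient's week-24 HbA1c, taken 20 weeks after the last dose, would count towards Trajenta's effectiveness.

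The safety endpoint is an incidence proportion (SAP 4.2), so no person-time denominator shows how much of the observation was exposed. For stoppers who stay under observation, the comparison of under 24 weeks with 24 weeks or more mixes two things: length of Trajenta use, and being on or off it when the event or value arose.

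**Working it through.** The plan has no figure of its own to reproduce. The 3,000 patients in Protocol 7.6 are a regulatory requirement without a formula. The check is arithmetic on the documents' own windows.

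**1. Off-drug share of a stopper's AE window**

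Inputs:
- Visit 3 at week *v* = 24 ± 2 (Protocol 6.2.2.3).
- AE collection to 7 days (1 week) after the last follow-up visit (Protocol 5.1.2.2).
- Stop at week *s* (assumed, shown as a range).

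If the patient is followed to Visit 3, the share is (*v* + 1 − *s*)/(*v* + 1). With *v* = 24 this is (25 − 4)/25 = 84% for *s* = 4 and (25 − 8)/25 = 68% for *s* = 8. If follow-up ends 7 days after stopping, the share is 1/(*s* + 1), so 1/5 = 20% for *s* = 4.

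| Stop at week | Visit 3 at week 22 | at week 24 | at week 26 | Follow-up ends 7 days after stop |
|---|---|---|---|---|
| 4 | 83% | 84% | 85% | 20% |
| 8 | 65% | 68% | 70% | 11% |
| 12 | 48% | 52% | 56% | 8% |
| 16 | 30% | 36% | 41% | 6% |
| 20 | 13% | 20% | 26% | 5% |

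With full follow-up, the share passes one half only when *s* < (*v* + 1)/2. That is week 12.5 for *v* = 24, and week 11.5 to 13.5 across the visit window. If the event rate were the same on and off drug (an assumption), these are also the expected shares of a stopper's AEs with onset off drug.

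**2. Whole cohort, for illustration**

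Assume 15% stop, all at week 8; neither figure is in the documents.
- All followed to week 25: 0.15 × 0.68 = 10.2% of observed time is off drug.
- Follow-up ends 7 days after stopping: 0.15 × 1/(0.15 × 9 + 0.85 × 25) = 0.15/22.6 = 0.7%.

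**3. Who is in the short-term set**

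The set is defined by administration under 24 weeks. Visit 3 may fall at weeks 22 to 26, so a patient still on drug, with administration recorded only to a Visit 3 at 22 to <24 weeks, also qualifies. Let *d* be the proportion stopping early and *q* the proportion of completers recorded below 24 weeks. The documents give neither. The stoppers' share of the set is *d*/(*d* + (1 − *d*)*q*). For *d* = 10% and *q* = 25% this is 0.10/(0.10 + 0.225) = 31%.

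| *d* | *q* = 0 | *q* = 10% | *q* = 25% | *q* = 50% |
|---|---|---|---|---|
| 10% | 100% | 53% | 31% | 18% |
| 20% | 100% | 71% | 50% | 33% |
| 30% | 100% | 81% | 63% | 46% |

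Stoppers are the whole set only if no completer is recorded below 24 weeks.

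**The case against.** **Follow-up after stopping is not stated.** The larger shares need observation to week 24 after the drug is stopped. Protocol 6.2.3 names premature discontinuation alongside the final visit as a point from which AEs already noted are followed to resolution. The flow chart records study completion at Visit 2 as well as Visit 3. Both fit follow-up that ends at stopping. On the other side, Protocol 6.2.2 follows enrolled patients for 24 weeks and both follow-up visits record changes in Trajenta. SAP 3.1 keeps only patients with completed safety follow-up but does not say what that means for a stopper. This objection stands as a limit on size: a week-4 stop gives anything from 20% to 84%.

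**Attribution is handled through causality.** Physicians judge causality using temporal relationship and dechallenge (Protocol 5.1.2.1). SAP 6.3.2 tabulates ADRs, causality and action taken beside all AEs. This stands in part, since AEs are not left wholly undifferentiated. But none of these tables uses time since the last dose, and the ADR definition removes only events rated unlikely.

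**The protocol itself uses the last visit.** Protocol 7.3.2 calculates HbA1c change to the last follow-up visit, so the SAP's rule for the change has protocol support. This stands. The clear mismatch is confined to the <6.5% response.

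**All AEs are the stated endpoint.** Protocol 5.1.1 and SAP 4.2 say so, and the study is descriptive. This stands against replacing the headline incidence, but not against adding a split beside it.

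**A reading the text does not bear out.** Protocol 3.2 says of AEs obtained from patients lost to follow-up: "This allows assessing the impact of informative censoring due to treatment discontinuation". A reader might infer that the missing on-drug/off-drug split leaves that purpose undone. The sentence concerns loss to follow-up and censoring, not onset relative to the last dose, and the split would not carry it out.

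**Conclusion.** The point holds in a limited form. The SAP does not tie AEs or HbA1c values to drug status, and it drops the on-treatment condition from the <6.5% response. For patients who stop early and remain under observation, the tables mix Trajenta with time off it. Off-drug time dominates a stopper's AE window only for stops before about week 12.5 with continued follow-up.

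The overall size cannot be fixed from the documents. Under the illustrative 15% stopping at week 8, off-drug time is between 0.7% and about 10% of all observed time, depending on follow-up.

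A reader might infer that the short-term row describes early stoppers, and so mostly time off the product. The documents do not support that. On-drug completers seen at weeks 22 to <24 can enter the set and may be the majority. That row may combine two different groups, which is a further reason to separate them. This is a cheap improvement in attribution; it does not invalidate the all-AE analysis.

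**What to change.** 1. **SAP 5.2 and 6.3:** keep the all-AE incidence as the stated endpoint. Beside it, add a split by onset: on treatment (first dose to last dose plus a residual interval that the sponsor states and justifies) versus later.
2. **SAP 5.1 and 6.2:** flag HbA1c and FPG values taken after the last dose, and report change and responder rates with and without them. Base the <6.5% response on values under treatment, as Protocol 5.2.1 defines it.
3. **Short-term set (SAP 6.2, 6.3.2):** show discontinuers separately from on-drug completers recorded at under 24 weeks.
4. **Follow-up:** state whether scheduled visits and AE collection continue after Trajenta is stopped, and what counts as completed safety follow-up for those patients.

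**Cost:** programming and extra table columns. AE onset is collected (Protocol 8.4.2) and total administration period is already reported (SAP 6.1), so last-dose timing should be derivable. The on-treatment incidence will be somewhat lower than the all-AE figure, so the two must be shown together and labelled clearly.

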6.1 Demographics and Baseline Characteristics

Data for the demographics and baseline characteristics in safety analysis set is demonstrated by descriptive statistics. In the descriptive statistics, number of subjects, mean, standard deviation, median, minimum and maximum will be calculated for continuous variables, and frequency and percentage will be presented for categorical variables.

The following demographics and baseline characteristics will be reported.

< Demographic information >

- Age, Gender, Pregnancy, Allergy, Height, Weight, Waist circumference, Smoking status, Diabetes mellitus complications and their classification, Other medical history and its classification, duration of T2DM, Family history, Pediatric group (Under 19 years), Geriatric group (65 years or older), Kidney disorder, Liver disorder, Subjects whose drug administration period of long-term (24 weeks or more)

< Medication information >

- Concomitant medication and its classification, Trajenta administration status (Total administration period of Trajenta, Total administration dose of Trajenta), Reason of prematurely study withdrawal, Other anti-diabetic agent and its classification

	CONFIDENTIAL :	Last Update Date
	THIS DOCUMENT AND INFORMATION CONTAINED HEREIN IS PROPRIETARY TO COMPANY AND IS NOT TO BE DISCLOSED WITHOUT THE WRITTEN PERMISSION OF COMPANY.	21-AUG-2017
STATISTICAL ANALYSIS PLAN(V3.0)		

6.2 Effectiveness Analyses

Effectiveness analysis shall be conducted for subjects of the effectiveness analysis set.

The change from baseline to last visit of HbA1c will be calculated for each subject. The difference of HbA1c between baseline and last visit shall be described by mean, and shall be analyzed with paired t-test.

According to the following baseline characteristics, the change from baseline to last visit of HbA1c will be analyzed with t-test or ANOVA (Analysis of Variance).

- Age, Gender, Pregnancy, Allergy, Diabetes mellitus complications and their classification, Other medical history and its classification, duration of T2DM, Family history, Pediatric group (Under 19 years), Geriatric group (65 years or older), Kidney disorder, Liver disorder, Subjects whose drug administration period of long-term (24 weeks or more), Concomitant medication and its classification, Total administration period of Trajenta, Reason of prematurely study withdrawal, Other anti-diabetic agent and its classification

If necessary, analysis for the impact of the change from baseline to last visit of HbA1c may be carried out using multiple regression analysis. In general, the variables corresponding to the baseline characteristics listed in section 6.1 are used as an independent variable. However, as considering the structure and characteristics of the collected data, the variables used for the actual analysis can be added or subtracted.

The frequency and percentage of the final effectiveness assessment will be summarized.

The final effectiveness assessment of “Improved” will be classified as “Effective”. The final effectiveness assessment of “No changed” and “Worsened” will be classified as “Ineffective”. The effectiveness rate and its 95% confidence intervals will be estimated with exact method.

The effectiveness rate will be analyzed according to the baseline characteristics listed in section 6.1. Chi-square test or Fisher’s exact test will be used for comparing between subcategories of each baseline characteristic and will be estimated with its 95% confidence interval.

According to the following subgroup, the frequency and percentage of subjects whose HbA1c of <

	CONFIDENTIAL :	Last Update Date
	THIS DOCUMENT AND INFORMATION CONTAINED HEREIN IS PROPRIETARY TO COMPANY AND IS NOT TO BE DISCLOSED WITHOUT THE WRITTEN PERMISSION OF COMPANY.	21-AUG-2017
STATISTICAL ANALYSIS PLAN(V3.0)		

6.5% at last visit and whose HbA1c lowering is at least 0.5% at last visit will be calculated. Additionally, the difference of FPG between baseline and last visit shall be analyzed with paired t-test.

- ① All of effectiveness analysis set
- ② Short-term effectiveness analysis set (Administration of Tragenta less than 24 weeks)
- ③ Long-term effectiveness analysis set (Administration of Tragenta for 24 weeks or more)
- ④ Subjects in effectiveness analysis set who administered DPP-4 inhibitor before administration of Tragenta
- ⑤ Subjects in effectiveness analysis set who did not administer DPP-4 inhibitor before administration of Tragenta

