5.1.2 Assessment of adverse events

5.1.2.1 Definitions of adverse events

Adverse event

An adverse event (AE) is defined as any untoward medical occurrence, including an exacerbation of a pre-existing condition, in a patient in a clinical investigation who received a pharmaceutical product. The event does not necessarily have to have a causal relationship with this treatment.

Serious adverse event

A serious adverse event (SAE) is defined as any AE which results in death, is immediately life-threatening, results in persistent or significant disability / incapacity, requires or prolongs patient hospitalisation, is a congenital anomaly / birth defect, or is to be deemed serious for any other reason if it is an important medical event when based upon appropriate medical judgement which may jeopardise the patient and may require medical or surgical intervention to prevent one of the other outcomes listed in the above definitions.

Adverse drug reaction

Adverse drug reaction (ADR) refers to any harmful, unintended reaction to the pharmaceutical product of any dose at which a causal relationship with the pharmaceutical product cannot be ruled out.

Non serious adverse drug reaction

Non serious adverse drug reaction is defined as any ADR which does not meet the SAE criteria.

Intensity of adverse event

The intensity of the AE should be defined based on the following three categories and according to medical and scientific judgment:

- Mild: Transient symptoms which are subjective or objective but no interference with the patient's daily activities. No change in dosage is needed to continue the treatment.
- Moderate: Marked symptoms with moderate interference with the patient's daily activities. Reduced dosage or unplanned treatment is necessary for the relief of adverse events.
- Severe: Considerable and unacceptable interference with the patient's daily activities. Discontinuation of the study drug is required because of significant adverse events.

To ensure that no confusion or misunderstanding of the difference between the terms 'serious' and 'severe' which are not synonymous, it should be noted that SAE does not necessarily correspond to serious or not serious AE to severe ones. All SAEs will be reported regardless of the intensity as mentioned above.

Causal relationship of adverse event

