6.3.1 Adverse Events by Demographics and Baseline Characteristics

For the AE(s) by demographics and baseline characteristics in the safety analysis set:

- The number of subjects to whom AE occurred and the number of AEs will be calculated.
- The incidence proportion of AEs and its 95% confidence interval will be estimated. Chi-square test or Fisher's exact test will be used for comparing between subcategories of each demographics and baseline characteristics.
- If necessary, analysis for the impact of the safety may be carried out using logistic multiple regression analysis. In general, the variables corresponding to the baseline characteristics listed in section 6.1 are used as an independent variable. However, as considering the structure and characteristics of the collected data, the variables used for the actual analysis can be added or subtracted.

	CONFIDENTIAL :	Last Update Date
	THIS DOCUMENT AND INFORMATION CONTAINED HEREIN IS PROPRIETARY TO COMPANY AND IS NOT TO BE DISCLOSED WITHOUT THE WRITTEN PERMISSION OF COMPANY.	21-AUG-2017
STATISTICAL ANALYSIS PLAN(V3.0)		

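### SAP 6.1 lists four variables known only after treatment starts as baseline characteristics, and SAP 6.2 and 6.3.1 test outcomes across them, so those p-values do not show risk factors or predictors of response

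*SAP*

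**What the plan says.** SAP 6.1 gives one list of demographics and baseline characteristics. Its demographic part includes the flag worded "Subjects whose drug administration period of long-term (24 weeks or more" (the same words appear in 6.2). Its medication part includes "Trajenta administration status (Total administration period of Trajenta, Total administration dose of Trajenta), Reason of prematurely study withdrawal". SAP 7.2 repeats all of these under its baseline heading.

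The list is then used in four places:

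- **HbA1c change (SAP 6.2):** t-test or ANOVA across a list that has the 24-week flag and ends with "Total administration period of Trajenta, Reason of prematurely study withdrawal, Other anti-diabetic agent and its classification". Total dose is not in it.
- **Effectiveness rate (SAP 6.2):** "The effectiveness rate will be analyzed according to the baseline characteristics listed in section 6.1", by chi-square or Fisher's exact test. This takes in all four variables.
- **AE incidence (SAP 6.3.1):** chi-square or Fisher's exact test, "comparing between subcategories of each demographics and baseline characteristics".
- **Regressions (SAP 6.2 and 6.3.1):** run if necessary. In general "the variables corresponding to the baseline characteristics listed in section 6.1 are used as an independent variable", though variables may be added or dropped.

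SAP 8 sets two-sided tests at 0.05. Protocol 7.1 makes all analyses descriptive and the p-values exploratory. Neither document marks the four variables as post-baseline or plans a landmark or exposure-adjusted analysis for them.

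**The concern.** A baseline characteristic is fixed before the outcome can act on it. These four are not. Protocol 5.1.1 makes AEs leading to discontinuation a safety endpoint, and Protocol 5.1.2.1 says of the severe grade: "Discontinuation of the study drug is required because of significant adverse events". An AE can therefore shorten treatment, and the plan then tests AE incidence by length of treatment. The effectiveness tests have the same weakness if a poor response leads the physician to stop the drug, a choice that Protocol 2.3 leaves open.

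At stake is how a by-characteristic table is read. A row headed as a baseline characteristic with p<0.05 invites the reading that short treatment is a risk factor for AEs, or long treatment a predictor of response. The same result can arise when exposure has no effect. Safety is the primary objective, so the AE table matters most.

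**Working it through.** **1. Where each variable is tested.**

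| Variable | SAP 6.1 and 7.2 | 6.2 HbA1c change | 6.2 effectiveness rate | 6.3.1 AE incidence | Default regressor |
|---|---|---|---|---|---|
| 24-week flag | yes | yes | yes | yes | yes |
| Total administration period | yes | yes | yes | yes | yes |
| Total dose | yes | no | yes | yes | yes |
| Reason for withdrawal | yes | yes | yes | yes | yes |

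The 6.3.1 column takes its wording to mean the 6.1 list. The last item in "Total administration period of Trajenta, Reason of prematurely study withdrawal, Other anti-diabetic agent and its classification", other anti-diabetic agents, is not one of the four.

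**2. Overlap.** The flag is a cut of the period. At 5 mg once daily (Protocol 4.1.3), 24 weeks is 24 × 7 × 5 = 840 mg, so total dose largely repeats the period.

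**3. Result by definition.** If withdrawal reasons include an adverse-event category (the documents do not list the categories), AE incidence in that category is about 100%. A test across withdrawal reasons then says nothing about risk.

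**4. Size of the AE artefact.** The documents give no AE rate, dropout rate or stopping share, so every input except n and the visit window is an assumption: n = 3,000; the same constant AE hazard for everyone, 15% by week 24; 15% other dropout by week 24; no effect of exposure; Visit 3 uniform over weeks 22 to 26 (the ±2-week window); AEs counted to Visit 3 plus 7 days, in line with Protocol 5.1.2.2; nobody removed; Pearson chi-square of AE by treatment below versus at or above 24 weeks.

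- Weekly hazard: −ln(0.85)/24 = 0.00677.
- Short group when no AE stops treatment: 3,000 × (0.15 + 0.85 × 0.5) = 1,725. Half of the completers fall below 24 weeks only because of the visit window.
- Overall incidence, mean window 24 + 1 = 25 weeks: 1 − exp(−0.00677 × 25) = 15.6%.

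| AEs that stop treatment | Incidence, <24 weeks | Incidence, ≥24 weeks | Runs with p<0.05 |
|---|---|---|---|
| 0% | 15.1% | 16.2% | about 15% |
| 10% | 16.1% | 14.9% | about 14% |
| 20% | 17.0% | 13.5% | about 73% |
| 40% | 18.7% | 10.8% | about 100% |

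Repeat runs agree within 0.1 point on incidence and give 13 to 15% for the last column at 0%. A valid test would reject in 5%.

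The overall figure does not move. At 0% it is (1,725 × 15.1% + 1,275 × 16.2%)/3,000 = 15.6%. At 20%, with about 1,763 patients in the short group, it is (1,763 × 17.0% + 1,237 × 13.5%)/3,000 = 15.6%. Only the split between the groups is distorted.

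**5. Dependence on the counting window.** If AEs are counted only to the end of treatment, the same inputs give 12.6 vs 15.5% at 0% stopping (p<0.05 in about 62 to 65% of runs, short treatment looking protective), 13.6 vs 14.3% at 10% (7 to 10%), 14.5 vs 12.9% at 20% (22 to 25%) and 16.4 vs 10.2% at 40% (about 100%). The sign can change with the window as well as with the stopping share.

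**6. HbA1c, same mechanism.** Assume 2,000 patients, mean change −0.6, between-patient SD 0.8, within-patient SD 0.5, and 10% stopping early at random. If a further 0 / 10 / 25% of those with no fall at week 12 stop, early stoppers look 0.00 / 0.24 / 0.50 points worse than the rest, with p<0.05 in 8 / 95 / 100% of runs. This compares early stoppers with all others. The 24-week cut would dilute the gap, because it also puts patients who complete in weeks 22 to 24 in the short group.

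**The case against.** The SAP never calls these variables risk factors or predictors. Protocol 7.1 and 7.2 make everything descriptive with no hypotheses, and both regressions are optional with an adjustable variable set. All of that stands. It limits the harm to exploratory tables and makes the regressions a default, not a fixed flaw. It does not make the t-tests and chi-square tests interpretable, since those are planned outright.

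Stronger readings that the documents do not support:

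- *Short treatment will always look harmful.* The table shows no such signal at 0% stopping and rejection well short of certain at 10%. The signal is clear only from about 20%, a share the documents do not give.
- *Moderate AEs also shorten exposure.* Protocol 5.1.2.1 says of that grade: "Reduced dosage or unplanned treatment is necessary for the relief of adverse events". Unplanned treatment does not shorten time on drug, and SAP 3.1 item 6 removes patients who did not follow the stated dosage. The argument rests on discontinuation.
- *Concomitant and anti-diabetic medication are also misfiled.* They are recorded at baseline and at both follow-ups, and the SAP does not say which time point is used. That is missing detail, not a shown error.
- *Leaving baseline HbA1c off the list makes the subgroup comparisons wrong.* Adjusted and unadjusted comparisons answer different questions in self-selected subgroups, and the documents do not settle which applies. It is a separate matter.

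**Conclusion.** The labelling point holds on the text alone: four variables that cannot be known at baseline are listed as baseline characteristics, and outcomes are tested across them. Because an AE can end treatment, and poor response may, p-values across these variables do not show risk factors or predictors of response.

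The size is not known. Under the stated assumptions, with no true effect, the AE test rejects in anything from about 14% to 100% of runs as the share of AEs ending treatment goes from 0 to 40%, and the direction reverses within that range.

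The reach is limited. Overall AE incidence, overall HbA1c change and comparisons by true baseline variables are not affected, and all the affected analyses are exploratory. The change is worth making because it is cheap and the tables would otherwise mislead. It does not threaten the study's main descriptive results.

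**What to change.** - In SAP 6.1 and 7.2, move the 24-week flag, total administration period, total dose and reason for premature withdrawal to a separate exposure and disposition list.
- Report outcomes by these four descriptively, without between-category tests.
- Remove them from the t-test/ANOVA list and the effectiveness-rate tests in 6.2, from the tests in 6.3.1, and from the default regressors of both regressions.
- Align the by-characteristic tables and regressions in 7.3 and 7.4, so that the SAP does not contradict itself.
- Keep the short-term and long-term AE tables in 6.3.2, which plan no between-group test.

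The cost is SAP wording, minor table changes on data already collected, and the loss of a few exploratory p-values.
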